### **3.3 Importance of Cell-Mediated Immune Responses in Controlling HPV-Associated Tumors**

Several lines of evidence highlight the importance of cell-mediated immune responses in controlling both HPV infections and HPV-associated neoplasms (for review, see (5)). First, the prevalence of HPV-related diseases (infections and neoplasms) is increased in transplant recipients on immunosuppressive therapies (6) and HIV-infected patients (7, 8), both of whom are known to have impaired cell-mediated immunity. HIV-infected women with baseline CD4+ T-cells of  $\geq 350$ , 200-349, and  $< 200$  cells per microliter had a 2.3, 3.0, and 7.7 times increase in invasive cervical cancer incidence, respectively, compared with HIV-uninfected women (9). HPV16 associated oropharyngeal cancer has been reported in the post-transplant setting (10) and the incidence of HPV16 associated tonsillar cancer in HIV infected men has been reported to be 2.6 fold greater (11) than in non-HIV infected individuals. In addition, when patients on immunosuppressive therapies discontinue their treatment, their HPV-associated lesions regress (for review, see (12)). Infiltrating CD4+ (T helper cells) and CD8+ (cytotoxic T cells) T cells have been observed in spontaneously regressing HPV-associated lesions (13). Lastly,

preclinical studies have demonstrated that vaccinated animals are protected from papillomavirus infection and from the development of neoplasms, and vaccination also facilitates the regression of existing lesions (14-16). The link between HPV16-associated lesions and/or carcinoma and cell-mediated immunity presents the possibility of eradicating these lesions or cancers through vaccines which enhance HPV-specific T cell immune responses.

### **3.4 HPV Oncogenic Proteins, E6 and E7, as Potential Targets for Immunotherapy Against HPV-Associated Cervical Cancer**

In the cellular progression from viral infection to malignant transformation, the episomal viral DNA can integrate into the host genome with a resultant deletion of non-critical viral genes. Expression of late genes (L1 and L2) and some early genes (E1 and E2) is typically lost, and E6 and E7 are often the only open reading frames consistently expressed in cancer cell lines (17) and in HPV-associated cancers (18), although they are expressed in productive precursor lesions. E6 and E7 are necessary for viral transformation through their inactivation of two human tumor suppressor proteins, p53 and pRb, respectively, resulting in dysregulated cell cycle proliferation, delayed cellular differentiation, increased frequency of spontaneous and carcinogenic-induced mutations, and increased chromosomal instability (19).

Since E6 and E7 are constitutively expressed in most HPV-associated cancers, they represent promising targets for the development of antigen-specific therapeutic vaccines. There are several advantages to targeting the E6 and/or E7 proteins. They are foreign viral proteins, and, therefore, are more immunogenic than a self-protein that is genetically altered (such as a mutated p53) or aberrantly reactivated (such as the embryonic protein, MAGE-1). Furthermore, since E6 and E7 are required for the induction and maintenance of the malignant phenotype of cancer cells (20), tumor cells cannot evade a directed immune response through antigen loss of E6 or E7. Lastly, preclinical studies suggest that vaccines targeting these early papillomavirus proteins can generate therapeutic as well as protective effects *in vivo* (21). Therefore, the E6 and E7 proteins represent logical targets for developing antigen-specific immunotherapies or vaccines directed against HPV-associated cervical cancers. Various forms of vaccines, such as vector-based vaccines, tumor-based vaccines, DNA-based vaccines and protein/peptide-based vaccines, have been described in experimental systems targeting the HPV16 E6 and/or E7 proteins (22-32).

### **3.5 Therapeutic Effects of the Standard Care of Chemoradiation for Cervical Cancer May be Improved by Therapeutic HPV Vaccines**

The current standard of care for advanced HPV-associated cervical cancer includes the use of a chemotherapeutic drug, cisplatin, in conjunction with local radiation therapy. Despite improvements noted with combination therapy, five-year survival in most patients affected by advanced cervical cancer is approximately 30% (33). Thus, an innovative treatment strategy, via a distinct mechanism, that can improve outcomes in patients with advanced cervical cancer is needed. We have previously demonstrated that administration of a therapeutic HPV vaccine following chemotherapy with cisplatin or

radiation was able to improve the therapeutic antitumor effect in a preclinical model compared to vaccination, chemotherapy or chemoradiation alone (34-36). These data suggest that a therapeutic HPV vaccine may have value in improving the therapeutic effect of the standard care of chemoradiation for cervical cancer.

### 3.6 Safety of TA-CIN Vaccine

TA-CIN is a single fusion protein comprised of HPV16 E6, E7 and L2 proteins linked in tandem. Vaccination with TA-CIN induces immunity to HPV16 E6/E7-specific T cell mediated immune responses and L2-specific neutralizing antibodies in mice. Importantly, vaccination of HPV16 infected-patients with TA-CIN is also designed to trigger therapeutic immunity targeting the E6, E7 and L2 of HPV16. A placebo-controlled, double-blinded phase I dose escalation study provided preliminary evidence that serial vaccination with up to 533 $\mu$ g of TA-CIN for a total of three doses in the absence of an adjuvant is safe, well-tolerated and immunogenic in healthy volunteers (37). However, vaccination of patients produced only low titers of L2-specific cross-neutralizing antibodies and weak E6/E7-specific interferon (IFN)- $\gamma$  and proliferative T cell responses following a TA-CIN dose response (37, 38). In a phase II clinical study, 29 patients with predominantly HPV16+ high grade vaginal or vulval intraepithelial neoplasia (VAIN or VIN), were vaccinated with 533  $\mu$ g of TA-CIN followed by a single dose boost with recombinant vaccinia virus expressing both HPV16 and HPV-18 E6 and E7 genes (TA-HPV) (2.5 x 10^5 pfu). Combination TA-CIN and TA-HPV vaccination failed to induce an improved rate of lesion regression as compared to earlier studies utilizing either TA-HPV alone or TA-CIN alone in 30 VIN patients (39).

Another clinical trial tested TA-CIN vaccination following **treatment** with an immunomodulatory drug, **imiquimod**. Twenty women aged 18–70 years with biopsy-proven VIN grades 2 and 3 were recruited (19 evaluated) in a clinical trial examining combination treatment with topical imiquimod followed by 3 doses of TA-CIN vaccination (40). Exclusion criteria were pregnancy, invasive disease, immunosuppression, history of severe allergy and previous HPV vaccination. Imiquimod 5% cream was self-administered topically for 8 weeks, escalating from one application in week 1 to two in week 2 and three applications in weeks 3–8. This was followed by three intramuscular doses of TA-CIN (128  $\mu$ g) at weeks 10, 14 and 18. The primary objective was to measure treatment effect on VIN by lesion size and histology and the secondary objectives were to assess lesion HPV status, symptoms, immune responses as well as safety, toxicity and tolerability. Women were reviewed at weeks 0, 10, 14, 18, 20, 26 and 52, the primary end point. Punch biopsies were taken for histology and HPV typing at weeks 0, 10, 20 and 52. Heparinized blood was obtained for immunological assays at weeks 0, 10 and 20. TA-CIN, which was administered intramuscularly into the deltoid muscle, was well tolerated with no side effects or adverse events (40).

[figure not shown]
The vaccination strategy of boosting with TA-CIN recombinant protein following priming with a different therapeutic HPV vaccine was investigated in a phase I clinical trial (41). 10 women with HPV16+ high grade VIN were primed with TA-HPV vaccinia vaccine followed by boosting with TA-CIN (533  $\mu$ g/0.5 mL) three times at 1 month

intervals 7-15 months after TA-HPV priming vaccination. The results showed that the prime-boost vaccination strategy elicited strong HPV16-specific proliferative T cell and serological responses. Furthermore, lesion shrinkage or symptom relief was observed in 3 patients. Importantly, vaccination with TA-CIN was shown to be safe and well tolerated with no reported adverse events. In sum, the four clinical trials involving the use of TA-CIN in over 90 patients provide strong support for the safety and feasibility of three monthly intramuscular TA-CIN vaccinations at doses as high as 533 $\mu$ g.

### 3.7 Rationale for the Clinical Trial Design

[figure not shown]
#### 3.7.1 TA-CIN is highly effective in tumor bearing mice but not in healthy mice

In a recent pre-clinical study, we have compared the HPV16-specific CD8 T cell immune responses elicited by three vaccinations with TA-CIN in the naïve or tumor bearing mice.

**Figure 1. TA-CIN is not immunogenic in healthy mice.** A. Schematic illustration of the experiment. Briefly, 5~8 weeks old female C57BL/6 mice (5 mice/group) were injected with either 25  $\mu$ g/mouse of TA-CIN or PBS on day 0. The mice were boosted twice with the same regimen in 2 week interval. On day 35, the mice were sacrificed and the spleens were harvested. B. Flow cytometry analysis of HPV16 E6 and E7-specific CD8+ T cell responses analyzed by IFN- $\gamma$  intracellular staining. Briefly, splenocytes were collected, stimulated with 1  $\mu$ g/ml HPV16 E6aa50-57, or E7aa49-57 peptide at the presence of GolgiPlug (1  $\mu$ l/ml) overnight at 37°C. The cells were then stained with anti-mouse CD8 followed by intracellular IFN- $\gamma$ . The data were acquired with FACSCalibur and analyzed with CellQuest. C. Summary of the flow cytometry data.

[figure not shown]
As shown in Figure 1, vaccination three times with TA-CIN alone is poorly immunogenic in healthy naïve mice. However, as shown in Figure 2, administration of TA-CIN to mice bearing HPV16 E6 and E7 expressing TC-1 tumor generated remarkably higher HPV16-specific CD8+ T cell responses as compared to the untreated mice. This was also associated with a potent therapeutic effect against the TC-1 tumor that had metastasized to lung. These results suggest that TA-CIN alone can be highly immunogenic and effective when administered into subject with preexisting exposure to HPV16-associated tumor.

**Figure 2. Therapeutic effect of TA-CIN against HPV16 E6E7-expressing TC-1 lung metastasis.** **A.** Schematic illustration of the experiment. Briefly, 5~8 weeks old female C57BL/6 mice (5 mice/group) were injected with 5  $\times$  10^4 TC-1 cells intravenously on day 0. On day 3, the mice were vaccinated with either 25  $\mu$ g/mouse of TA-CIN via subcutaneous injection or left untreated. The mice were boosted twice with the same regimen. On day 21, the mice were sacrificed, lungs and spleens were harvested. The weight of the lungs was weighed, and the number of nodules of the tumor was counted. **B.** Images of lungs of the mice from the experiment. **C.** Summary of the weight of the lungs of the mice from the experiment. **D.** Summary of the number of TC-1 metastasis nodules. **E.** Flow cytometry analysis of HPV16 E6 and E7-specific CD8 $^+$  T cell responses analyzed by IFN- $\gamma$  intracellular staining. Briefly, splenocytes were collected, stimulated with 1  $\mu$ g/ml HPV16 E6aa50-57, or E7aa49-57 peptide at the presence of GolgiPlug (1  $\mu$ l/ml) overnight at 37 $^\circ$ C. The cells were then stained with anti-mouse CD8 followed by intracellular IFN- $\gamma$ . The data were acquired with FACSCalibur and analyzed with CellQuest. **F.** Summary of the flow cytometry data.

### 3.7.2 Site of Vaccination Affects the Anti-Tumor Immunity

In another pre-clinical study, we explored whether the site of vaccination will impact anti-tumor immunity, specifically whether intramuscular vaccination of the leg will generate better anti-tumor immunity than vaccination on the arm against cervical HPV disease. As a model for vaccination of cervical cancer patients in the arm versus the leg, we vaccinated mice bearing cervicovaginal, luciferase-expressing TC-1 tumor with a therapeutic HPV16 DNA vaccine pNGVL4A-CRT/E7(detox), administered either in the front leg (which drains to a lymph node distal to the cervical tumor) or the hind leg (which drains to the proximal lymph node shared with the cervical tumor).

[figure not shown]

**Figure 3. Characterization of therapeutic antitumor effect of therapeutic HPV vaccine administered at different site in cervicovaginal tumor model.** 5~8 weeks old female C57BL/6 mice (5 mice/group) were injected with  $5 \times 10^4$  of TC-1/ luciferase cells at the intravaginal cavity on day 0. The mice were vaccinated with 20  $\mu$ g/mouse of pNGVL4a-CRT/E7 DNA via intramuscular injection follow by electroporation at different site on day 4 and boosted once 4 days later. (A) Bioluminescence images of the cervicovaginal TC-1/luciferase tumor-bearing mice. (B) Kaplan-Meier survival of the TC-1/luciferase tumor-bearing mice.

As shown in Figure 3, tumor bearing mice that received hind leg vaccination demonstrated a significantly greater reduction in luminescence signal as compared to the tumor bearing mice vaccinated at the front leg or tumor bearing mice with no vaccination, corresponding to a greater reduction in tumor volume. Furthermore, 100% of the tumor bearing mice with hind leg vaccination survived for at least 80 days while 80% of the tumor bearing mice with front leg vaccination and 100% of the tumor bearing mice with no vaccination died within 50 days after tumor challenge, demonstrating a significantly better anti-tumor effect against cervicovaginal tumor elicited by the therapeutic vaccination when administered at the hind leg of the tumor bearing mice.

To examine the impact of the site of vaccination upon antigen-specific immune response in mice bearing cervicovaginal tumor, we harvested the tumor and lymph nodes from the tumor bearing mice that received no vaccination, vaccination in front leg, or vaccination in hind leg 7 days after the last vaccination and analyzed each sample for E7-Specific CD8+ T cells. As shown in Figure 4 A-B, mice vaccinated at the hind leg generated significantly larger amount of E7-specific CD8+ tumor infiltrating lymphocyte as compared to mice vaccinated at the front leg.

When comparing the T cell populations in the lymph nodes, vaccination in the hind leg generated a significantly higher amount of E7-specific CD8+ T cells in the inguinal and iliac lymph node as compared to the axillary lymph node, while vaccination in the front leg generated comparable amount of E7-specific CD8+ T cells in the axillary, inguinal, and iliac lymph nodes (Figure 4 C-D). These results suggest that administration of a therapeutic HPV vaccine such as TA-CIN at a site adjacent to tumor-draining lymph nodes can enhance the generation of antigen-specific T cells and improve treatment outcome.

**Figure 4. Characterization of E7-Specific CD8+ T cells in tumor and lymph node microenvironment produced by different vaccination sites in TC-1 tumor-bearing mice.** 5~8 weeks old female C57BL/6 mice (5 mice/group) were injected with  $5 \times 10^4$  of TC-1/ luciferase cells at the intravaginal cavity on day 0. The mice were vaccinated with 20  $\mu$ g/mouse of pNGVL4a-CRT/E7 DNA via intramuscular injection follow by electroporation at different site on day 4 and boosted once 4 days later. 7 days after the last vaccination, lymph nodes and tumors from different groups (both treated and untreated) were harvested, processed, and analyzed for HPV16 E7-specific CD8+ T cells by HPV16 E7 peptide-loaded tetramer staining followed by flow cytometry analysis. **(A-B)** Representative flow cytometry image and Bar graph showing E7-specific CD8+ T cells in TC-1 tumor tissues. **(C-D)** Representative flow cytometry image and Bar graph showing E7-specific CD8+ T cells in inguinal lymph nodes, iliac lymph nodes and axillary lymph nodes. (\* =  $p < 0.05$ , \*\* =  $p < 0.01$ , ns = not significant).

## 4. PARTICIPANT SELECTION

### 4.1 Inclusion Criteria

- 4.1.1 Females, age  $\geq$  18 years
- 4.1.2 Diagnosis of HPV16 related stage IB1-IV cervical cancer (**Appendix A**); completed definitive treatment within the past 12 months
- 4.1.3 No evidence of disease recurrence based on imaging and clinical assessments within 8 weeks of enrollment
- 4.1.4 Documented to have HPV16 nucleic acid within the cervical tumor specimen as determined by *in situ* hybridization. **NOTE:** HPV16 nucleic acid testing may be done as part of a “pre-screening” consent at any time prior to enrollment on the primary study. To be eligible for HPV16 testing, patients must have stage IB1-IV cervical cancer and have completed definitive treatment such that enrollment within 12 months of diagnosis would be possible if testing is positive.
- 4.1.5 Fresh-frozen or paraffin-embedded material must be available for *in situ* hybridization testing for HPV16 nucleic acid for central confirmation.
- 4.1.6 Eastern Cooperative Oncology Group (ECOG) performance status of 0 or 1 (**Appendix B**)
- 4.1.7 Adequate organ function as defined by the following parameters:
  - white blood cell count  $\geq$  3,000
  - lymphocyte number  $\geq$  500
  - absolute neutrophil count  $\geq$  1,000
  - platelets  $\geq$  90,000
  - hemoglobin  $\geq$  9
  - total bilirubin  $<$  1.5 X upper limit of normal (ULN)  
( $<$  3 x ULN if Gilbert’s disease)
  - AST(SGOT)/ALT(SGPT)  $<$  3 X ULN
  - creatinine  $<$  1.5X ULN or estimated creatinine clearance  $\geq$  60 ml/min per Modified Cockcroft-Gault Formula
- 4.1.8 Ability to understand and the willingness to sign a written informed consent document
- 4.1.9 Subject is able to adhere to the study visit schedule and other protocol requirements

### 4.2 Exclusion Criteria

- 4.2.1 Patients with a diagnosis of immunosuppression or prolonged, active use of immunosuppressive medications such as systemic steroids

- 4.2.2 Patients who have had chemotherapy, radiation, biological cancer therapy, or other investigational agents within 28 days prior to the first dose of study drug
- 4.2.3 Patients who have had surgery within 28 days of dosing of investigational agent, excluding minor procedures (dental work, skin biopsy, etc)
- 4.2.4 Patients with an uncontrolled intercurrent illness including, but not limited to, ongoing or active infection, symptomatic congestive heart failure, unstable angina pectoris, cardiac arrhythmia, or psychiatric illness/social situations that would limit compliance with study requirements
- 4.2.5 Patients who have an active autoimmune disease (e.g., rheumatoid arthritis, systemic lupus erythematosus (SLE), ulcerative colitis, Crohn's Disease, multiple sclerosis (MS), ankylosing spondylitis)
- 4.2.6 Patients being chronically treated with immunosuppressive drugs such as cyclosporin, adrenocorticotrophic hormone (ACTH), or systemic corticosteroids
- 4.2.7 Patients with a recognized immunodeficiency disease including cellular immunodeficiencies, hypogammaglobulinemia or dysgammaglobulinemia; patients who have acquired, hereditary, or congenital immunodeficiencies
- 4.2.8 Women of child-bearing potential (i.e., those who have had fertility-sparing procedures for the management of cervical cancer) will be excluded
- 4.2.9 Patient with active or chronic infection of HIV, HCV, or HBV (tested at baseline; see Study Calendar)
- 4.2.10 Patients with non-healed wounds
- 4.2.11 A history of current or recent concurrent malignancy ( $\leq 5$  years) except basal cell cancer.
- 4.2.12 Inability to understand or unwillingness to sign an informed consent document

### **4.3 Inclusion of Women and Minorities**

Only women are eligible for this trial as cervical cancer does not afflict males. Women of all races and ethnic groups are eligible for this trial.

## 5. REGISTRATION PROCEDURES

### 5.1 General Guidelines

**Pre-Screening:** Patients eligible for HPV16 testing must be entered on study centrally at the Sidney Kimmel Comprehensive Cancer Center at the Johns Hopkins University. All sites should call the Lead Study Coordinator/designee at the Coordinating Center. The fax cover sheet, Pre-Screening Registration Form, and Pre-Screening Eligibility Worksheet will be supplied to each participating site.

**Primary Study:** Eligible patients will be entered on study centrally at the Sidney Kimmel Comprehensive Cancer Center at the Johns Hopkins University. All sites should call the Lead Study Coordinator/designee at the Coordinating Center to verify drug availability. The fax cover sheet, Registration Form, and Eligibility Worksheet will be supplied to each participating site. If a patient does not receive protocol therapy following registration, the patient's registration on the study may be canceled. The Study Coordinator should be notified of cancellations as soon as possible.

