Safety assessments will continue for a period for 1 month after the last vaccination; reporting requirements, exclusions, and stopping rules are outlined (**Sections 7 and 8**). Subjects who withdraw from the study for reasons other than toxicity may be replaced at the discretion of the Principal Investigator and/or IND sponsor.

Few or no serious adverse events (SAEs) are expected from this regimen and routes of administration. The motivation for the design is to confirm that the dose and site of injection implemented here has minimal or no systemic toxicity, as well as determining the preferred injection site that can elicit more potent immune response.

Patient immune and clinical responses in cohorts with different injection sites will be evaluated through the following methods: 1) peripheral blood lymphocytes (PBL) to assess HPV16 E6 and E7-specific CD8 $^{+}$  T cell ELISPOT and lymphocyte proliferative responses to HPV16 antigenic stimulation and T cell receptor sequencing; 2) serum for HPV16 L2, E6, and E7 and neutralizing antibody responses; 3) plasma for residual HPV viral load; and, 4) imaging scans per standard-of-care (i.e., every 6-12 months) and as clinically indicated to assess time to disease recurrence.

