## 2. OBJECTIVES

### 2.1 Primary Objectives

- 2.1.1 To determine the safety and feasibility of intramuscular administration of TA-CIN vaccine via arm or thigh in patients with a history of HPV16 associated IB1-IV cervical cancer

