### 6.2 Blinding and Randomization

This is a non-blinded, non-placebo controlled, randomized, prospective study. Eligible patients will be randomized in a 1:1 ratio to receive TA-CIN in either the arm or the thigh. Randomization will occur after registration and prior to the planned first dose of TA-CIN. All participants and providers will know the arm to which subjects are randomized.

A master list of randomization assignments will be generated and will be delivered to the Research Pharmacy at each participating site and to other key personnel, as identified. Upon successful registration of a subject, randomization will occur by the appropriate study staff.

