### 12.2 Sample Size

A total of 15 patients with a history of advanced HPV16-related cervical cancer will be enrolled and randomized at 1:1 ratio to receive TA-CIN administrations via thigh (Group A) or arm (Group B). Each group will treat at most 7 patients. A previous study by Smyth *et al.* in non-cancer patients who did not receive chemo/radiotherapy showed that 9 out of 25 patients had a detectable E6/E7-specific T cell response one month after TA-CIN vaccination. It is expected that the prior chemo/radiotherapy received by the cervical cancer patients enrolled on this study will prime the response to the TA-CIN such that the T cell response rate will be higher. If the true response rate is 65% for Group A and 45% for Group B, with 7 patients each group, there is about 70% chance of picking the correct injection site based on the observed number of responders in the two groups. Even if the true response rate is 60% for Group A and 45% for Group B, with 7 patients each group, there is still about 60% chance to correctly pick the winner.

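### Unblinded discretion to cancel undosed patients after randomisation and to replace non-toxicity withdrawals, with no analysis set, can tilt a site choice made on raw response counts

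*Combined protocol and SAP*

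**What the plan says.** Four parts of the protocol bear on who counts at each injection site.

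- **Cancellation (Section 5.1).** "If a patient does not receive protocol therapy following registration, the patient's registration on the study may be canceled". No criteria are given, and patients already randomised are not excepted.
- **Replacement (Section 1).** "Subjects who withdraw from the study for reasons other than toxicity may be replaced at the discretion of the Principal Investigator and/or IND sponsor". There is no cut-off by dose or time, and no statement of which assignment the replacement receives.
- **Order and blinding (Section 6.2).** "Randomization will occur after registration and prior to the planned first dose of TA-CIN". Also: "All participants and providers will know the arm to which subjects are randomized". The allocation list "will be delivered to the Research Pharmacy at each participating site and to other key personnel".
- **Use of the counts (Section 12).** Section 12.5 picks the better site on the observed number of responses, without a formal test. Sections 12.1 to 12.5 define no analysis population. They do not say how a cancelled, withdrawn or replaced patient is counted. On group size, Section 12.2 says "Each group will treat at most 7 patients", while Section 12.4 gives 7 to 8 per cohort; both give 15 enrolled.

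The primary objective in Section 2.1 is "To determine the safety and feasibility of intramuscular administration of TA-CIN vaccine via arm or thigh". Feasibility by site is therefore something the trial sets out to report.

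**The concern.** Randomisation protects the comparison of arm with thigh only if membership of each group is fixed by the assignment. Here two later decisions can change it, and both are taken by people who know the assignment. Before dosing, a patient who learns her site and does not proceed can have her registration cancelled. After dosing, a patient who withdraws from the study for a reason other than toxicity can be replaced or not, as the investigator or sponsor chooses. By then samples may already exist, since the Section 10 calendar draws immune samples at Weeks 5 and 9. Whether toxicity was the reason is also judged with the assignment known.

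The selection rule has no denominator. Removing a patient, adding one, or keeping both a patient and her replacement therefore changes the count directly. With about 7 patients per site, a single patient matters. Section 1 says that these results, together with the toxicity data, will choose the site for later trials. The feasibility objective is also affected: refusals of the assigned site and incomplete courses are feasibility outcomes, and no rule requires them to be counted by site.

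**Working it through.** **Inputs.** From Section 12.2: 7 patients per group; true response rates of 65% (Group A, thigh) against 45% (Group B, arm), or 60% against 45%; stated chances of a correct pick of about 70% and about 60%. From Section 12.5: the comparison is of observed numbers of responses. Two assumptions are added: an equal-rate case at 45%, which is the lower rate in the plan's own scenarios, and the replacement of one dosed non-responder by a new patient with the same true rate.

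**1. The plan's figures.** With independent X_A ~ Bin(7, p_A) and X_B ~ Bin(7, p_B),

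P(A leads) = Σ over i > j of C(7,i) p_A^i (1−p_A)^(7−i) × C(7,j) p_B^j (1−p_B)^(7−j).

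- 65% v 45%: A leads 69.3%, tie 15.8%. The plan says about 70%.
- 60% v 45%: A leads 62.1%, tie 17.9%. The plan says about 60%.

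Both agree when a correct pick means a strict lead.

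**2. Equal rates, no replacement.** At 45% v 45%, each site leads outright with probability 39.5%, and 21.1% are ties.

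**3. One non-responder replaced.** The count at that site becomes Y = X + Z if X ≤ 6, and Y = 7 if X = 7, with Z ~ Bernoulli(p).

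| True rates | Replacement at | Leading outright, before | Leading outright, after |
|---|---|---|---|
| 45% v 45% | one site | that site 39.5%, other 39.5% | that site 48.9%, other 31.2% |
| 65% v 45% | worse site | better site 69.3% | better site 60.0% |
| 60% v 45% | worse site | better site 62.1% | better site 52.6% |

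The shifts are 48.9 − 39.5 = 9.4 points, 69.3 − 60.0 = 9.3 points and 62.1 − 52.6 = 9.5 points.

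**4. Replaced patient kept in the count.** Section 1 does not say that her data are dropped. If she stays, 8 patients are compared with 7, and the count at her site is X + Z in all cases. This differs from step 3 only when all 7 respond, which at 45% has probability 0.45^7 = 0.4%. The results agree to the rounding shown: 48.9% v 31.2% at equal rates, and 60.0% at 65% v 45%. The tilt arises on either reading, so long as raw counts decide.

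**5. The same unequal groups compared on proportions.** With 8 v 7 at equal 45% rates, the larger group leads 48.9% and the smaller 51.0%; ties almost vanish. With 7 at 65% and 8 at 45%, the better site leads 78.0%. The comparable figure for 7 v 7 with ties split evenly is 69.3 + 15.8/2 = 77.2%. Proportions remove the advantage of size.

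**6. The undosed route.** Cancellation comes before any vaccine, so it can depend on the assignment and the patient's characteristics but not on her response. It can still unbalance the count. If one place is left unfilled at 65% v 45%, 6 v 7 gives 56.3% when the loss is at the better site, and 7 v 6 gives 78.1% when it is at the worse site.

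**The case against.** The strongest reply is that the text is silent rather than wrong. To replace a patient is not to delete her, and to cancel a registration is not to remove the patient from reports. That is fair, but step 4 shows that keeping a replaced patient gives the same tilt under a raw count, so the silence itself is the defect.

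Several stronger readings are tempting and are not supported.

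- **That failures are hidden.** Section 5.1 requires the Study Coordinator to be told of cancellations. Section 11.2 puts retention and adherence on the weekly agenda, and Section 11.3 sends a summary of withdrawals to the Medical Expert Committee. What is missing is a rule to count and report them by site.
- **That early leavers are unlikely to be responders.** The patient-level definition in Section 12.1 uses the maximum increase after dosing. With samples at Weeks 5 and 9, a patient who stops after one or two doses could already qualify.
- **That anyone who stops treatment can be replaced.** Recurrence, immune-suppressive drugs and non-compliance end treatment under Section 6.9, but Section 6.10 plans follow-up to 24 months. Replacement needs withdrawal from the study.
- **That several replacements at one site are realistic.** Two replaced dosed patients would mean 9 treated there and 16 overall, beyond Section 12.4's 7 to 8 per cohort and the total of 15. One makes 8 and 15, which fits Section 12.4 but exceeds the cap of 7 in Section 12.2.

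That this is a pilot does not dispose of the point: the protocol chose to randomise, and its result feeds the choice of site.

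**Conclusion.** The point holds as a gap in the design. The protocol permits unblinded, discretionary changes to who is counted at each site after assignment, and Section 12 supplies no analysis set to neutralise them. One patient's replacement moves the selection probabilities by about 9 points, in a plan whose own chance of a correct pick is only about 60% to 70%.

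That size rests on 7 per site, the plan's response rates (or 45% at both), and a replaced patient who is a non-responder, or one who is kept so that 8 are compared with 7 on counts. The dropped non-responder is an illustrative worst case, not a forecast. A reader might infer that the choice of site will be biased, or that staff will select patients by outcome. The documents show neither. The tilt could favour either site, and cancellation before dosing cannot depend on response.

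**What to change.** The changes are to wording only.

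- **Section 5.1:** allow cancellation only before randomisation.
- **Section 1:** replace the discretionary rule with an automatic one. Only a randomised patient who receives no dose is replaced, and her replacement receives the same site assignment so that group sizes hold. Taking the next assignment on the list instead could give groups of 6 and 8; on raw counts at equal 45% rates, the larger would lead 58.4% to 22.7%.
- **Section 12.5:** keep every patient with at least one dose in the safety and immune-response counts of her assigned site. Pick the winner on the proportion of responders whenever group sizes differ. State in advance how a dosed patient without a post-dose sample is counted, because Section 10 allows research samples to be omitted.
- **Feasibility (Section 2.1):** report by site the numbers randomised, never dosed, and given 1, 2 and 3 doses. A patient who declines her site still leaves the immune comparison, but is then visible where she belongs.
- **Sections 12.2 and 12.4:** reconcile at most 7 with 7 to 8 per group, and say whether replaced patients count toward the 15.

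The costs are small. Observed response and completion rates may be slightly lower because early withdrawals stay in, and giving a replacement the same site makes that one assignment predictable.
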